10.6 Performance Status

Patients will be graded according to the Zubrod performance status scale.

POINT	DESCRIPTION
0	Fully active, able to carry on all pre-disease performance without restriction.
1	Restricted in physically strenuous activity but ambulatory and able to carry out work of a light or sedentary nature, e.g., light housework, office work.
2	Ambulatory and capable of self-care but unable to carry out any work activities; up and about more than 50% of waking hours.
3	Capable of limited self-care, confined to bed or chair more than 50% of waking hours.
4	Completely disabled; cannot carry on any self-care; totally confined to bed or chair.

11.0 STATISTICAL CONSIDERATIONS

11.1 General Overview

The overall goal of this study is to determine and compare the progression-free survival (PFS) of two different doses of carfilzomib in combination with dexamethasone in multiple myeloma (MM) patients with relapsed and/or refractory disease. This study is based on a randomized Phase II design to determine whether the higher dose level of carfilzomib in combination with dexamethasone yields a better outcome as measured by PFS. Patients will be randomly assigned with equal allocation to one of the two dose levels of carfilzomib in combination with dexamethasone. The treatment arm with the lower carfilzomib dose will be denoted Arm 1 and the treatment arm with the higher carfilzomib dose will be denoted Arm 2.

11.2 Sample Size and Power Justification

Sixty-three eligible patients will be accrued to each treatment arm unless undue toxicity is encountered. The study anticipates an accrual of 72 eligible patients per year, based on recent ECOG accrual estimates for intergroup trials in this patient population. Thus 126 patients will be accrued in approximately 1.75 years. The study anticipates accruing an additional 14 patients to account for ineligibilities and withdrawal of consent for a total of 140 patients.

A median PFS of 9 months is anticipated in Arm 1, based on previous trials using this treatment combination in this patient group (Onyx, personal conversations). With 1.75 years of patient accrual and 1.5 years of follow-up 63 patients per arm results in a study with 90% power to detect a hazard ratio of 1.67, which corresponds to an increase in median PFS from 9 months to 15 months in Arm 2, the arm with the higher carfilzomib dose. These calculations are based on a one-sided stratified log rank test at level (alpha) of 0.1 and on the assumption that progressions are exponentially distributed.

11.3 Analysis of Primary Endpoint

Efficacy analysis will be performed on intent to treat basis. Progression-free survival will be assessed in each arm using the method of Kaplan Meier and compared between arms using the stratified long-rank test. Assuming exponential progression-free survival, uniform recruitment of 72 patients a year, an accrual period of 1.75 years and a follow-up period of 1.5 years, 100 progressions are expected to occur within 3.25 years. The analysis for the primary endpoint will be performed after 100 progressions have been observed, but no later than 2 years follow-up of the last patient.

11.4 Interim Analysis for Futility

An interim analysis for futility will be performed after approximately half the number of events has been observed. Based on the alternative hypothesis and the assumption that events are exponentially distributed, 50 progressions are expected to occur within 20 months or one year and 8 months. At this time the 96% confidence interval of the observed hazard ratio will be calculated based on the log-rank statistics. If the alternative hypothesis is within this confidence interval it will be concluded that the alternative hypothesis cannot be rejected and the study will continue as planned; otherwise the rejection of the alternative hypothesis would lead to early termination and the conclusion that dexamethasone in combination with the higher carfilzomib dose (Arm 2) is not better than dexamethasone in combination with the lower carfilzomib dose (Arm 1). The actual decision to terminate the study early will be made by the Data and Safety Monitoring Committee, and will consider toxicity and other endpoints. Since only futility is being tested the significance level alpha is not affected by this interim analysis. Also, the effect on overall power of the study is minimal.

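### The futility rule in Section 11.4 gives no direction, so as worded it also stops the trial, with the conclusion that Arm 2 is not better, when the 96% interval lies wholly above HR 1.67

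*Combined protocol and SAP*

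**What the plan says.** Section 11.4 places one interim look at about half the events: "An interim analysis for futility will be performed after approximately half the number of events has been observed". Half of the planned 100 progressions (Section 11.3) is 50. At the look a 96% confidence interval for the hazard ratio is computed from the log-rank statistics. The rule then has two branches:

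- **Continue.** "If the alternative hypothesis is within this confidence interval it will be concluded that the alternative hypothesis cannot be rejected", and the study goes on as planned.
- **Stop.** "otherwise the rejection of the alternative hypothesis would lead to early termination", and the conclusion attached to stopping is that Arm 2 is not better than Arm 1.

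The section adds three statements. On type I error it says: "Since only futility is being tested the significance level alpha is not affected by this interim analysis". Its remark about the cost of the look in power reads: "Also, the effect on overall power of the study is minimal". As to who decides: "The actual decision to terminate the study early will be made by the Data and Safety Monitoring Committee", which will also weigh toxicity and other endpoints.

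Section 11.2 supplies the alternative as a single number: "90% power to detect a hazard ratio of 1.67", equated with medians of 9 months in Arm 1 and 15 months in Arm 2. Since 15/9 = 1.67, the ratio is Arm 1 relative to Arm 2, and values above 1 favour the higher dose. The final test is directional: "These calculations are based on a one-sided stratified log rank test at level (alpha) of 0.1".

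**The concern.** A two-sided interval can miss a given value from either side. The stop branch takes in every case where the alternative is outside the interval, and nothing confines it to intervals lying below 1.67. An interval lying wholly above 1.67 therefore falls in the stop branch too, and the sentence attaches to it the conclusion that Arm 2 is not better. That is the reverse of what such data would show.

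This is at odds with the section's heading, its statement that only futility is tested, the one-sided final test, and the aim in Section 11.1 of finding out whether the higher dose does better. What is at stake is a written decision rule that gives the wrong answer in one region. The futility method itself is not in question.

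**Working it through.** **Inputs.** Hazard ratio 1.67, one-sided alpha 0.10, power 90%, 63 patients per arm and medians of 9 and 15 months (Section 11.2); equal allocation (Section 11.1); 100 final events, 1.75 years of accrual and 1.5 years of follow-up (Section 11.3); 96% interval and 50 interim events at 20 months (Section 11.4).

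**The plan's own figures.**

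- Events required: 4 × (1.2816 + 1.2816)² / (ln 1.67)² = 26.28 / 0.2630 = 99.9, so 100.
- Power with 100 events: Φ(ln 1.67 × √100 / 2 − 1.2816) = Φ(2.564 − 1.282) = 0.900.
- With exponential times and uniform accrual of 126 patients over 21 months, the expected number of events under the alternative is 50.2 at 20 months and 100.6 at 39 months.

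The design figures reproduce.

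**Where the rule stops.** At 50 events SE(log HR) = 2/√50 = 0.2828. A 96% interval leaves 2% in each tail, so z = 2.054 and the half-width is 2.054 × 0.2828 = 0.581. The value 1.67 is outside the interval when the observed ratio is

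- below exp(ln 1.67 − 0.581) = 0.934, or
- above exp(ln 1.67 + 0.581) = 2.985.

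The look is only approximately at half the events, and the result does not depend on exactly 50: the limits are 0.905 and 3.081 at 45 events, and 0.960 and 2.906 at 55.

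**Worked case.** For an observed ratio of 3.0 at 50 events the interval is exp(ln 3 ± 0.581) = 1.68 to 5.36, and Z against a ratio of 1 is ln 3 / 0.2828 = 3.88. Read literally, the sentence says stop, Arm 2 not better.

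**Probability of stopping at 50 events**, from log HR ~ N(ln true HR, 0.2828²):

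| True HR | Lower side | Upper side |
|---|---|---|
| 1.0 | 40.5% | 0.006% |
| 1.2 | 18.8% | 0.06% |
| 1.4 | 7.6% | 0.4% |
| 1.67 | 2.0% | 2.0% |

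**Rejection at the final test if the rule were applied mechanically**, from the bivariate normal distribution of Z at 50 and 100 events (correlation √0.5, critical value 1.282):

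| True HR | No look | Lower side only | Both sides |
|---|---|---|---|
| 1.0 | 10.0% | 9.8% | 9.8% |
| 1.67 | 90.0% | 89.5% | 87.5% |

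A simulation of 4 million trials at 1.67 gave 0.9003, 0.8947 and 0.8746. The loss at 1.67 is 0.9002 − 0.8945 = 0.6 points for the one-directional rule and 0.9002 − 0.8745 = 2.6 points for the literal one. The plan's remark that the power loss is minimal is correct for the one-directional rule.

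Beyond the design effect the literal rule behaves perversely. At a true ratio of 2.0 the upper-side stop has probability 7.8%, and power is 90.6% against 98.4% with the lower side only. This matters only as a sign that the literal rule cannot be the intended one.

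**The case against.** The strongest reply is that the section settles the direction itself. It is headed as a futility analysis, says only futility is tested, and attaches a single conclusion to stopping. The stop branch also turns on rejecting the alternative. In a one-sided superiority design the alternative can be read as a ratio of at least 1.67, and an interval wholly above 1.67 does not reject that. On this reading the upper stop disappears. The intent is indeed clear. However, the documents never state the alternative in that form, and asking whether it lies within an interval fits a single value more naturally.

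Second, the rule is not automatic. The committee decides, and it is hard to imagine one declaring no benefit at Z near 3.9. This stands: the 87.5% figure describes mechanical application, which the plan does not prescribe, and should be read as hypothetical.

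Third, the case of 3.0 is marginal. Its lower limit clears 1.67 by only 0.01 with the standard error 2/√50. In a simulation of the design the Cox standard error near an observed ratio of 3 was about 0.308, giving roughly 1.59 to 5.65, which contains 1.67. This also stands for that example, but not for the point. Section 11.4 specifies log-rank statistics, and the simulated upper-side probability at 1.67 was about 2.1% with the log-rank and 1.8% with the Cox interval. A less marginal value, 3.5, gives exp(ln 3.5 ± 0.581) = 1.96 to 6.26.

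Fourth, accrual has been permanently closed by memorandum, so a change may come too late to matter. The documents do not say whether the look took place.

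**Conclusion.** The concern holds as a defect of wording, and it is small. With the alternative taken as the printed value of 1.67, the stopping sentence covers observed ratios above about 2.99 at 50 events as well as those below about 0.93, and it gives the wrong conclusion for the upper group. The upper-side stop is rare at or below the design effect (at most 2.0%), type I error is not inflated, and a wrong stop is unlikely in practice.

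The size rests on the approximation SE = 2/√events with equal allocation, on the normal approximation for the log hazard ratio, and on a look at 45 to 55 events. The finding itself rests on reading the alternative as a single value, the only form the documents give.

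**What to change.** Replace the two-branch sentence with a directional one, for example: *Stop for futility only if the upper limit of the two-sided 96% confidence interval for the hazard ratio (Arm 1 relative to Arm 2) is below 1.67; otherwise continue.* Naming the direction of the ratio matters, because on the inverse scale the alternative is 9/15 = 0.60 and the limits swap roles.

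This keeps the futility boundary already implied (about 0.93 at 50 events) and the 2% chance of a futility stop under the alternative. Alpha, sample size and timing do not change. The cost is one sentence. If the look has already taken place, one line in the report stating which rule was applied is enough.

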11.5 Analysis of Secondary Endpoints

Secondary efficacy endpoints include response rate (PR or better) and overall survival (OS). All efficacy analyses will be performed on intent to treat basis. The response rate (sCR, CR, VGPR, PR) for each arm will be determined by the number of patients achieving a response as defined in Section [10.3](#) divided by the number of patients assessed for response in each arm and compared between arms using Fisher's exact test.

The response rate for patients who relapse on Arm 1 and cross-over to Arm 3 will also be determined in order to determine whether response can be re-captured for those patients by increasing the carfilzomib dose.

Overall survival will be assessed in each arm using the method of Kaplan Meier and compared using the stratified log-rank test.

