- 11 Pre-study (within 14 days prior to registration), then on Day 1 (\pm 3 days) of Cycles 2-12, then monthly until disease progression, at disease progression and at all follow up visits.
- 12 See Section [15.2](#).
- 13 Every 3 months after removal from protocol therapy for up to 3 years after initial registration, or more often if clinically indicated. For study purposes, response assessments (SPEP, immunoglobulins, 24 hour urine, serum/urine IFE, and CRP) are no longer required after progression or removal from trial due to toxicity.
- 14 See Section [7.0](#).
- 15 See Section [8.5](#) for treatment modification for cardiopulmonary events.
- 16 Unless otherwise noted, all required studies are to be performed on Day 1 of the treatment cycle.
- 17 At the time of progression, patients on Arm 1 may cross-over to Arm 3, providing they meet the additional criteria outlined in Section [5.2](#).
- 18 For patients with extramedullary progression (EMP), a follow-up PET scan at the end of treatment or at the time of VGPR, whichever occurs earlier, is required. See Sections [15.1](#) and Appendix [18.2](#) for requirements.
- 19 For patients that crossover to Arm 3, return to Cycle 1, Day 1, and follow the same study calendar. Assessments completed at time of progression on Arm 1, do not need to be repeated on Arm 3 (crossover) C1, D1, provided that ANC, platelets, SGOT, SGPT, serum creatinine, SPEP, and lambda light chain assessments are accomplished within 14 days prior to registration to Arm 3. All other assessments may have been accomplished anytime within 28 days prior to registration to Arm 3 (i.e. at time of progression on Arm 1). Note: Per eligibility criterion 5.2b, at least 14 days and no more than 28 days must have elapsed between the last day of treatment on Arm 1 and registration to Arm 3.

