Increasing Disease (INC): First objective status recorded (other than Unknowns or those before three weeks) of Progression, provided this occurs within eight weeks of registration.

Inadequate Assessment. Response Unknown (NASS): Progression greater than eight weeks after registration and either all objective statuses prior to registration are unknown or the only known objective statuses occurred less than three weeks after registration.

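### Section 11.5 promises intent-to-treat efficacy analyses, but its next sentence divides the response rate by patients assessed for response, an undefined group that depends on events after randomisation.

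*Combined protocol and SAP*

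**What the plan says.** Section 11.5 sets the population for the secondary efficacy endpoints: "All efficacy analyses will be performed on intent to treat basis". The next sentence defines the response rate for each arm as the number of patients with sCR, CR, VGPR or PR under Section 10.3, "divided by the number of patients assessed for response in each arm", and compares arms with Fisher's exact test. It states no significance level or sidedness for that test.

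Three other places bear on who is assessed:

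- **Study Calendar (Section 9.0), footnote 11.** After baseline, response tests fall on Day 1 "of Cycles 2-12, then monthly until disease progression, at disease progression and at all follow up visits". The first scheduled on-treatment assessment is therefore Cycle 2 Day 1.
- **Study Calendar, footnote 13.** Response assessments "are no longer required after progression or removal from trial due to toxicity".
- **Section 10.3.** The category for inadequate assessment, NASS, is defined as "Progression greater than eight weeks after registration and either all objective statuses prior to registration are unknown", or the only known statuses fell less than three weeks after registration.

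**The concern.** The two adjacent sentences in 11.5 give the same answer only if every randomised patient is assessed, and nothing in the protocol guarantees that. Under intent to treat, a patient who dies or withdraws before a response test counts as a non-responder. Under the stated formula that patient leaves the denominator and the rate goes up.

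Objective 1.2a asks for response rates to be evaluated in each arm as well as compared. An inflated rate is therefore a problem even when the loss is the same in both arms. A reader told that the analysis is intent to treat would not expect the published percentage to be conditional on having been assessed.

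**Working it through.** The plan states no response rate, power or sample size for this endpoint, so there is no figure of its own to reproduce. The check is textual first, then arithmetic on the size.

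**1. Is the group defined anywhere?** No. Section 11.8 names the toxicity-evaluable set and 11.6 names its cardiac analysis sets, but the response denominator has no counterpart. Section 10.3 lists best-response categories and does not say which of them count in a denominator. NASS requires progression more than eight weeks after registration. A patient who dies, withdraws or is removed before any post-baseline assessment, with no documented progression, fits no category.

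**2. Can such patients occur?** Yes, although this is not the usual course. Cycle 2 Day 1 is about four weeks in. Section 7.6 allows earlier removal (unacceptable toxicity, permanent discontinuation of carfilzomib, withdrawal). Footnote 13 then drops response tests for a patient removed for toxicity. On the other side, 7.3a and 8.3a normally carry a patient with related severe toxicity in Cycle 1 into a second cycle, and so to the first scheduled assessment.

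**3. Effect on an arm's rate.** Let n be the patients randomised to the arm, R the responders and u the share unassessed. An unassessed patient cannot be a documented responder, so R is the same either way.

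- Intent-to-treat rate = R/n
- Rate as written = R/[n(1-u)]
- Ratio = 1/(1-u)
- u = 5%: 1/0.95 = 1.05
- u = 10%: 1/0.90 = 1.11

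The documents give no u. As an illustrative value only, Section 11.2 says: "The study anticipates accruing an additional 14 patients to account for ineligibilities and withdrawal of consent for a total of 140 patients". That is 14/140 = 10%, or 7 of 70 per arm. With 22 responders in an arm (assumed), 22/70 = 31.4% and 22/63 = 34.9%, a gap of 3.5 points.

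**4. Effect on the comparison.** Assumptions: 70 randomised per arm, the same true response rate in both arms, 14 unassessed in total and all of them non-responders, and a one-sided Fisher test at 0.10 looking for a higher rate in Arm 2. Responders in an arm with d assessed follow Binomial(d, 70p/d). The exact false-positive rates are:

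| Unassessed, Arm 1 v Arm 2 | p = 25% | p = 35% | p = 50% |
|---|---|---|---|
| 7 v 7 | 0.070 | 0.072 | 0.066 |
| 6 v 8 | 0.089 | 0.086 | 0.101 |
| 5 v 9 | 0.100 | 0.117 | 0.144 |
| 4 v 10 | 0.137 | 0.157 | 0.199 |

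With nobody unassessed and p = 35%, the figure is 0.069. Balanced loss leaves the test essentially unchanged (0.072). A clear imbalance does not.

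**The case against.** The strongest reply is that, coming straight after the intent-to-treat sentence, the phrase may be loose wording for the patients in each arm, or for those with measurable disease, which Section 5.1b requires of everyone. That reading is possible, but the text does not state it, and a programmer following the formula as written would drop unassessed patients.

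A second reply is that 7.1c calls for response assessments when the dose is modified, so early toxicity would trigger one. That paragraph deals with laboratory results in cycles after Cycle 1, and with dose modification rather than removal. It does not guarantee an assessment for a patient who leaves in Cycle 1. What does stand is that 7.3a and 8.3a make such removal the exception.

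A reader might infer more than the documents support:

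- **That the comparison is biased towards the higher dose.** No difference in loss between arms is shown. Cycle 1 carfilzomib dosing is the same in Arms 1 and 2, and the first scheduled assessment comes before the doses diverge.
- **That about 10% will be unassessed.** The 14 of 140 is an allowance for ineligibility and consent withdrawal. Section 14.1 requires data on ineligible patients, so they need not be unassessed.
- **That a patient whose only status is progression before three weeks is lost from the denominator.** The increasing-disease category does set such statuses aside ("other than Unknowns or those before three weeks) of Progression, provided this occurs within eight weeks of registration"), but that patient has been assessed and stays in as a non-responder. The missing label is a separate matter.
- **That the crossover response rate has the same fault.** Section 11.5 names that population separately ("The response rate for patients who relapse on Arm 1 and cross-over to Arm 3 will also be determined") and does not attach the assessed-only denominator to it.

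**Conclusion.** The conflict in wording is certain: Section 11.5 states a denominator that does not follow its own intent-to-treat rule, and no other section reconciles the two. The consequence is conditional and probably modest. Each arm's rate is inflated by 1/(1-u), which is nothing if all patients are assessed, 5% in relative terms at u = 5% and 11% at u = 10%. These values of u are assumptions.

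Any material effect on the Fisher test needs an imbalance between arms that the documents do not show. The test figures also rest on assumed response rates, splits of the loss, level and sidedness. The endpoint is secondary, and the PFS analysis, futility rule and sample size do not use this denominator. The text should be corrected, but the point does not threaten the trial's main conclusion.

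**What to change.** In Section 11.5, replace the denominator with all randomised patients in the assigned arm, in line with the sentence before it. State that patients with no or inadequate response assessment, including NASS, count as non-responders. Report the assessed-only rate as a sensitivity analysis, with the number unassessed in each arm and the reasons.

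This takes two or three sentences and no new data, since Section 14.1 already requires submission for every registered patient. The price is somewhat lower reported rates. Ineligible patients are also counted, including any without measurable disease in whom response cannot be determined. Against a denominator of eligible patients only, the planned 10% allowance lowers the rate by a factor of at most 126/140 = 0.90. The fall could be larger, because the June 2016 closure memorandum records more ineligibility than anticipated.

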6.0 STRATIFICATION FACTORS

At registration patients will be randomized to receive Dexamethasone + either Low Dose or High Dose Carfilzomib. A dynamic allocation scheme will be used to balance treatment by the following two stratification factors:

1 - 3 prior therapies vs. 4-6 prior therapies.

Refractory to bortezomib vs. not refractory to bortezomib.

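### Response rate is tested with an unstratified Fisher's exact test although allocation, PFS and OS use two stratification factors: valid, but conservative, and cheap to improve

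*Combined protocol and SAP*

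**What the plan says.** Section 6.0 states: "A dynamic allocation scheme will be used to balance treatment by the following two stratification factors". The factors are "1 - 3 prior therapies vs. 4-6 prior therapies" and "Refractory to bortezomib vs. not refractory to bortezomib", which makes four cells.

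Section 11.3 has PFS "compared between arms using the stratified long-rank test" (a typing slip for log-rank), and Section 11.5 has OS "compared using the stratified log-rank test". The same Section 11.5 has response rates "compared between arms using Fisher's exact test" and mentions neither strata nor covariates.

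Section 11.2 fixes the size: "Sixty-three eligible patients will be accrued to each treatment arm unless undue toxicity is encountered". It sets one-sided alpha 0.10 for PFS. For the response comparison the plan gives no alpha, sidedness, expected rates or power, and no reason for leaving the strata out.

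**The concern.** Comparing response rates between arms is the first secondary objective in Section 1.2. Two features of the planned test cost power.

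- Fisher's test is discrete, so at 63 per arm its actual type I error lies below the nominal level.
- If allocation is balanced on factors that predict response, a pooled 2×2 analysis overstates the null variance of the difference, and the test becomes more conservative still.

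At stake is a missed difference in response that the same data could have shown. A false positive is not at stake. Both factors are already collected for allocation, so using them needs no new data.

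**Working it through.** **1. The plan's own figures.** None is stated for the response test, so the nearest stated ones were checked.

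- *PFS.* Exponential PFS with medians of 9 and 15 months, 21 months of uniform accrual and 18 months of follow-up gives 100.6 expected events (plan: 100). Power = Φ(√d/2 × ln HR − 1.2816) = Φ(5.016 × 0.5108 − 1.2816) = Φ(1.281) = 90.0% (plan: 90%).
- *Cardiac toxicity, Section 11.6.* For 8% against 23% with 63 per arm, one-sided 0.10, exact enumeration of Fisher's test gives 80.0% (plan: 79%). The uncorrected normal approximation gives 85.7%. The stated figure is therefore close to Fisher's test, which already shows several points lost against an asymptotic test at this sample size.

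**2. Conservatism from discreteness.** Exact enumeration, 63 per arm, equal true rates of 20% to 50%: Fisher's actual one-sided size is 0.065 to 0.073 at nominal 0.10. For a 20-point difference its power is 77% to 85%, against 82% to 89% for the unstratified chi-square.

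**3. Conservatism from ignoring the strata.** With four equal cells balanced between arms, the pooled test uses p̄(1−p̄), while the true null variance uses the mean of pₛ(1−pₛ). Take assumed rates of 65/40/30/10%:

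- p̄ = 0.3625, so p̄(1−p̄) = 0.2311.
- Mean pₛ(1−pₛ) = (0.2275 + 0.2400 + 0.2100 + 0.0900)/4 = 0.1919.
- Ratio 0.830, square root 0.911. The pooled cut-off of 1.2816 acts like 1.2816/0.911 = 1.407, a one-sided size of about 8.0%.

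Simulation gives 8.2% for the unstratified chi-square. If all four rates are equal the ratio is 1 and this cost vanishes.

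**4. Power side by side.** Assumed, because the documents do not give them: control rates by cell, near-equal cells balanced between arms, odds ratio 2.5, one-sided 0.10, 63 assessed per arm. There were 40,000 simulated trials per scenario. The unstratified chi-square separates the two causes: chi-square minus Fisher is discreteness, and CMH minus chi-square is stratification.

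| Control response by cell | Fisher | Chi-square, unstratified | CMH, uncorrected | Total gap | Discreteness | Strata |
|---|---|---|---|---|---|---|
| 65/40/30/10% | 73.6% | 79.7% | 84.9% | 11.3 | 6.1 | 5.2 |
| 55/35/35/15% | 79.7% | 84.6% | 87.8% | 8.1 | 4.9 | 3.2 |
| 35% in all | 84.8% | 88.6% | 88.6% | 3.8 | 3.8 | 0.0 |

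With 65/40/30/10%, actual size is 5.8% for Fisher and 9.6% for CMH. Across the three scenarios CMH runs at about 9.6% to 10.3%.

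**5. Sensitivity to the assumptions.** At odds ratio 2 with the 65/40/30/10% rates, power is 52.8% (Fisher) and 67.8% (CMH), a gap of 15.0 points. With unequal cells (shares 35/25/15/25%) and odds ratio 2.25:

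| Prognostic odds ratio per factor | Fisher | Chi-square | CMH | Discreteness | Strata |
|---|---|---|---|---|---|
| 1 | 77.0% | 81.8% | 81.9% | 4.8 | 0.1 |
| 2 | 73.4% | 79.1% | 81.9% | 5.7 | 2.8 |
| 4 | 61.9% | 69.4% | 76.6% | 7.5 | 7.2 |

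The 4-to-11-point range therefore belongs to odds ratio 2.5 and the rates in step 4. Other assumptions reach about 15. In this setting CMH size was about 9.5% to 10.9%.

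**6. Which stratified test.** A separate run of 8,000 trials with the step 4 inputs compared Fisher, the stratified exact test and uncorrected CMH:

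- 65/40/30/10%: 73.8 / 79.8 / 84.6%.
- 55/35/35/15%: 79.8 / 83.7 / 88.0%.
- No stratum effect: 85.3 / 85.5 / 89.3%.

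A continuity-corrected CMH gains nothing when the factors are not prognostic (84.9% against 84.8% for Fisher). At two-sided 0.05 with odds ratio 2.25 it is then slightly worse (53.9% against 57.2%).

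**The case against.** Fisher's test on the pooled table controls type I error, needs no large-sample argument and contradicts nothing else in the plan. The plan claims no power for response, so no stated property fails, and even the level used above is borrowed from PFS. The response rates, cell sizes and prognostic strength are assumed. The endpoint is secondary in a Phase II trial whose primary test is already stratified. All of this stands, and it makes the point minor.

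Three stronger readings are tempting, and the documents do not support them.

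- *The test is invalid.* It is not: its size lies below nominal in every null scenario run.
- *The whole power gap comes from ignoring the strata.* Much of it is discreteness, which an unstratified chi-square would also remove. With non-prognostic factors, all of it is.
- *Any stratified test recovers the gap at no cost.* The exact and continuity-corrected versions give back much or all of it.

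What the objection does not answer is why response alone, of the three efficacy comparisons, leaves out factors that the plan uses for allocation and for the other two.

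**Conclusion.** The point holds as a minor improvement. The planned response test is valid but conservative. With 63 per arm, one-sided 0.10 and odds ratio 2.5, it has about 4 to 11 points less power than an uncorrected CMH test. Of these, about 4 to 6 points are due to discreteness and 0 to about 5 to the omitted strata. The second part exists only if the factors predict response, and the documents do not say how strongly they do. That the plan stratifies PFS and OS by these factors suggests that it regards them as relevant to outcome, but does not show that they predict response. The simulations also assume balance within all four cells, while the dynamic scheme in Section 6.0 is described only as balancing on the two factors. The primary endpoint is unaffected.

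**What to change.** In Section 11.5, replace Fisher's test for the Arm 1 versus Arm 2 response comparison with a CMH test without continuity correction, stratified by the two Section 6.0 factors. State its alpha and sidedness. Report a stratified odds ratio or risk difference with a confidence interval, and keep Fisher's test as a sensitivity analysis. Name in advance the condition, such as sparse cells, under which the exact stratified version is used. Make the change before response is compared by arm.

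The cost is a sentence or two and no new data. The downside is that the CMH test is asymptotic (about 9.6% to 10.3% actual size at nominal 10% in the step 4 scenarios), and that falling back on the exact version gives up much of the gain. If Fisher's test is kept as the main analysis, a sentence saying that it is meant as a simple descriptive comparison would at least explain the difference from PFS and OS.
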